7.5 Follow-up of Adverse Events

In the case of an SAE, the subject must be followed up until recovery is complete in terms of clinical and laboratory parameters, or until the event has stabilised. Follow up may continue after completion of protocol treatment if necessary. Follow-up information on any SAE will be documented using the SAE Form and sent to the BILCAP Study Office.

7.6 Expected Adverse Reactions

The common toxicities of capecitabine are plantar/palmar erythema (57%), diarrhea (47%), nausea (35%), stomatitis (23%), vomiting (18%), fatigue (16%), abdominal pain (11%), asthenia (10%) and myelosuppression. Less common toxicities are detailed on the product Summary of Product Characteristics (SPC) at http://emc.medicines.org.uk/.

8 OUTCOME MEASURES

8.1 Primary outcome measure

Length of survival: Survival will be calculated from the time of randomisation to the date of death (from any cause) or censor date (date last seen alive). All patients will be followed up for at least 2 years for this primary analysis.

8.2 Secondary outcome measures

5-year survival rates: Survival will be calculated from the time of randomisation to the date of death (from any cause) or censor date (date last seen alive). All patients will be followed up for at least 5 years for this secondary analysis.

Relapse free survival: Disease recurrence will be assessed during the first 5 years after randomisation. Relapse-free survival is defined as the time between the date of randomisation and the date of documented disease recurrence (if this occurs within 5 years) or disease related death.

Toxicity in the treatment arm will be analysed in terms of the incidence, severity, type, causality and duration.

Quality of Life (QoL) will be assessed using EORTC QOL Questionnaire (QLQ-C30 version 3) with the EORTC QLQ-LMC21 site-specific add-on, and EuroQoL (5 questions).

Health care economics will be assessed using the BILCAP health problems questionnaire as well as additional data on required supportive care from the treatment and follow-up forms.

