2.2 Secondary objectives

To assess:

- (i) The effect of adjuvant capecitabine on 5-year survival rates
- (ii) The effect of adjuvant capecitabine on relapse free survival
- (iii) The toxicity associated with adjuvant capecitabine
- (iv) The impact on quality of life (QoL) of capecitabine compared to observation
- (v) The health economic aspects of adjuvant capecitabine compared to observation

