3 STUDY DESIGN

3.1 Type of Study

This is a multicentre, prospective, randomised phase III trial of patients who have undergone a macroscopically complete surgical resection of a biliary tract cancer. Those patients who fulfil the inclusion criteria will be stratified by surgical centre, tumour site (hilar/extrahepatic cholangiocarcinoma, intrahepatic cholangiocarcinoma, lower common bile duct cholangiocarcinoma and gall bladder carcinoma), and by the type of resection (RO/R1) and performance status (ECOG PS 0,1,2), and randomised to either:

Treatment arm: Capecitabine 1250 mg/m² given post-operatively twice a day on day 1 to 14 of

a 3 weekly cycle for 24 weeks (8 cycles).

Control arm: No scheduled post-operative chemotherapy.

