5.10 Discontinuation of Treatment

A patient should discontinue study treatment in the event of any of the following:

- due to a toxicity as described in Section 5.5, Table 5.1, or the SPC for capecitabine.
- development of a life-threatening toxicity
- due to a treatment delay due to toxicity of longer than 2 weeks (see section 5.5)
- if relapse is documented
- administration of any other anti-tumour chemotherapy, radiotherapy or investigational agent during the study treatment period.
- pregnancy
- any other reason given by the investigator
- patient decides to discontinue study treatment
- patient withdraws consent to participate in trial (see Section 10.6)

Full details of the reasons for discontinuation or withdrawal of the trial drug should be recorded on the relevant CRF if clinician-initiated. If it is the patient's decision a simple statement reflecting patient preference will suffice.

All patients, including those who were withdrawn from trial treatment, should be followed-up in accordance with the protocol, unless the patient has withdrawn their consent. In this case no more data will be gathered on the patient; however all information up until the patient's retraction of consent will be used.

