9 STATISTICAL CONSIDERATIONS

9.1 Randomisation & Stratification

Participating oncology or surgical centres will randomise patients into the trial. A 1:1 treatment randomisation will be performed. Treatment will not be blinded. Patients will be stratified by surgical centre, tumour site (hilar/extrahepatic cholangiocarcinoma, intrahepatic cholangiocarcinoma, lower common bile duct cholangiocarcinoma or gall bladder carcinoma) and by the type of resection (RO/RI) and performance status (ECOG PS 0,1,2).

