9.3 Analysis

The primary analysis will be comparison of overall survival across treatment groups, calculated from the time of randomisation to the date of death (or censor date). All analysis will be on an intention to treat basis. Comparison of survival estimates will be by log-rank analysis. Toxicity and response rates will be compared across treatment groups using Pearson's chi-square test. QoL scores will be calculated according to the EORTC C30 manual and EuroQoL guidelines and compared across treatment groups using standardised area under the curve analyses and Mann-Whitney tests. Cox proportional hazards models will be undertaken to determine prognostic factors and their influence on survival and provide an adjusted treatment effect by important prognostic and stratification factors.

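### Relapse-free survival in section 8.2 leaves out deaths not attributed to the disease: a misnamed secondary endpoint that rests on unblinded attribution of cause of death, with a probably modest effect on the results

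*Protocol*

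**What the plan says.** Section 2.2 lists among the secondary objectives "The effect of adjuvant capecitabine on relapse free survival". The only definition is in section 8.2: time from randomisation to the "date of documented disease recurrence (if this occurs within 5 years) or disease related death". The study summary and section 1.3 merely name the endpoint.

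Section 8.1 runs overall survival to the "date of death (from any cause) or censor date (date last seen alive"), and section 8.2 repeats that rule for 5-year survival. The restriction to deaths attributed to the disease thus appears for RFS alone.

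On analysis, section 9.3 says "Comparison of survival estimates will be by log-rank analysis" and "All analysis will be on an intention to treat basis". It does not say what happens in the RFS analysis to a patient who dies of something else. Section 9.1 says "Treatment will not be blinded". No section says who decides that a death is disease related, or that the decision is made without knowledge of the arm.

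**The concern.** An endpoint called relapse-free survival is normally read as being alive without relapse. Under section 8.2, a patient who dies without documented recurrence, of toxicity or of another illness, has not failed. There are three consequences.

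- **Level.** If these patients are censored at death, a survival curve treats them as still able to relapse later. It then estimates freedom from relapse in a setting without other deaths, which is at or above the proportion alive and relapse-free.
- **Comparison.** Controls have "No scheduled post-operative chemotherapy" (section 3.1), while section 5.10 lists "development of a life-threatening toxicity" among the reasons to stop capecitabine. Drug deaths before recurrence can therefore arise only in one arm. If they occur in excess, leaving them out makes the RFS hazard ratio more favourable to capecitabine than an all-cause RFS would be.
- **Attribution.** Section 1.1 says that most patients with biliary tumours die of sepsis, usually through poor biliary drainage. Section 5.6 says that obstruction usually signals recurrence but can be benign. A septic death without documented recurrence could be put down to cancer, benign obstruction or drug toxicity, and that open-label judgement decides whether an event exists.

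A smaller flaw is that the 5-year limit is attached to recurrence but not to disease-related death. A relapse at 5.5 years is ignored, yet the death that follows from it counts.

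**Working it through.** The protocol states no RFS rate, event count or power, so there is no RFS figure to reproduce. From section 9.2 the check borrows the design hazard ratio of 0.71 (ln 0.32 / ln 0.20 = 0.708) and the control 2-year survival rates of 20% to 40% that it considers.

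**Assumptions, not in the documents**
- 2-year freedom from relapse S(24) of 20% or 40%, matching that survival range
- constant hazards
- non-disease death hazard h of 0.1% to 0.4% per month
- non-disease deaths censored under the current definition

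**Level of RFS.** The relapse hazard is λ = -ln S(24)/24, which is 0.0671 per month at 20% and 0.0382 at 40%. Freedom from relapse at 5 years is S(24)^2.5, which is 1.8% and 10.1%. True RFS at month t is S(t) × exp(-ht), so the overstatement is S(t) × (1 - exp(-ht)). The omitted share of events is h/(h + λ).

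The factor 1 - exp(-ht) at h = 0.001 and 0.004 is 0.0237 and 0.0915 at 24 months, and 0.0582 and 0.2134 at 60 months.

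| 2-year freedom from relapse | Overstated at 2 years | Overstated at 5 years | Events omitted |
|---|---|---|---|
| 20% | 0.5-1.8 points | 0.1-0.4 points | 1.5-5.6% |
| 40% | 0.9-3.7 points | 0.6-2.2 points | 2.6-9.5% |

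For example, at 40% and h = 0.004 the 2-year overstatement is 0.40 × 0.0915 = 0.037, and the omitted share is 0.004/(0.004 + 0.0382) = 9.5%. The overstatement is proportional to S(t), so it is larger if freedom from relapse is better than assumed.

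**Hazard ratio.** The model has 205 patients per arm (410 randomised equally, section 3.2), exponential relapse times, 5 years of follow-up, and toxic deaths confined to the first 6 months of the capecitabine arm. The HR is approximated by the ratio of event rates. The current definition returns the relapse HR unchanged. Counting all deaths gives the values below. Ranges cover control 2-year freedom from relapse of 20% and 40%, with no other-cause deaths.

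| Toxic deaths | All-cause HR when relapse HR is 0.71 | All-cause HR when relapse HR is 1.0 |
|---|---|---|
| 0% | 0.710 | 1.000 |
| 1% | 0.717-0.718 | 1.008-1.010 |
| 2% | 0.723-0.727 | 1.017-1.020 |
| 5% | 0.744-0.753 | 1.044-1.052 |

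This is about 0.01 per 1% of toxic deaths. With a 20% control rate and relapse HR 0.71, 2-year RFS on capecitabine falls from 31.9% to 31.6%, 31.3% and 30.3% at 1%, 2% and 5% toxic deaths.

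A separate effect should not be confused with this one. Adding the same other-cause hazard of 0.03 per year to both arms, with no toxic deaths, leaves an HR of 1.0 at 1.0. It moves 0.71 to 0.720-0.728, because deaths unaffected by treatment dilute a real benefit. That is a difference in what is estimated, not a tilt caused by drug deaths.

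**The case against.** The strongest reply is that little rests on this endpoint. RFS is one of several secondary outcomes. The primary endpoint and 5-year survival count every death, and the sample size in section 9.2 is built on overall survival. That stands, and it sets the severity.

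A reader might infer that the definition hides harm from capecitabine. The documents do not support this. A drug death counts in overall survival, enters the toxicity analysis by severity and causality (section 8.2), is reportable as a serious adverse event for at least 9 months after randomisation (section 7) and comes before the data and safety monitoring committee (section 9.4).

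A reader might also infer that capecitabine is favoured as a matter of fact. That holds only if non-disease deaths are more frequent in that arm. The protocol gives no such rate, and comorbid or late postoperative deaths can occur in both arms.

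Larger figures are tempting too. With 5-year freedom from relapse of 35%, the same hazards give an overstatement of 2.0 to 7.5 points. Under constant hazards, however, the 2-year rates used here imply only 1.8% to 10.1% at 5 years. The top hazard is itself generous: 1 - exp(-0.24) is about 21% non-disease mortality over 5 years, in a trial that excludes serious uncontrolled conditions (section 4.2).

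The protocol does not state that these deaths are censored or that a Kaplan-Meier RFS curve will be shown. A log-rank test that censors them validly compares cause-specific hazards, and handling rules often sit in a statistical analysis plan, which is not shown here. That is fair for the censoring detail. It does not rescue the event definition, which the protocol states and such a plan would have to overrule.

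The intention-to-treat statement is not contradicted: it governs who is analysed in which arm, not which deaths are events. The 5-year limit on recurrence follows the scanning schedule in section 6.5, and the mismatch probably concerns few patients.

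**Conclusion.** The point holds as a flaw in the definition of a secondary endpoint and should be fixed. What section 8.2 defines is closer to time to recurrence or disease-related death than to relapse-free survival. It departs from the all-cause rule used beside it for survival, and it lets unblinded attribution decide events.

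The size is unknown from the documents and probably modest. The 2-year and 5-year overstatements (0.5-3.7 and 0.1-2.2 points) and the omitted share of events (1.5-9.5%) depend on constant hazards, the assumed relapse and death rates, and censoring of the omitted deaths. The hazard-ratio shift from drug deaths (roughly 0.01-0.05 for 1-5% toxic deaths) is conditional, and that component is zero if no such excess occurs. The conclusion on overall survival is untouched.

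**What to change.** In section 8.2, and in any analysis plan that follows it:

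- Define RFS as time from randomisation to the first of documented recurrence or death from any cause.
- Censor patients alive without recurrence at their last disease assessment.
- Apply the 5-year limit to both components.
- If the present version is still wanted, keep it as a supporting endpoint under its own name (time to recurrence or disease-related death), with other deaths as competing events.

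The cost is a change of wording. Deaths are already collected through national statistics flagging with death certificates (section 9.5), and scans are already scheduled to 5 years (section 6.5), so no new data are needed. The downside is that reported RFS will be slightly lower.

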9 STATISTICAL CONSIDERATIONS

9.1 Randomisation & Stratification

Participating oncology or surgical centres will randomise patients into the trial. A 1:1 treatment randomisation will be performed. Treatment will not be blinded. Patients will be stratified by surgical centre, tumour site (hilar/extrahepatic cholangiocarcinoma, intrahepatic cholangiocarcinoma, lower common bile duct cholangiocarcinoma or gall bladder carcinoma) and by the type of resection (RO/RI) and performance status (ECOG PS 0,1,2).

9.2 Sample Size

The primary outcome measure is overall survival with sample size calculations based on comparison of two-year rates. The two-year survival rates achieved in the control arms of the one phase III trial in biliary tract cancer is around 20% (Takada et al 2002). The aim of this trial is to increase this to 32% using capecitabine. In order to detect this 12% increase with a 2-sided significance level of 5% and 80% power, 360 patients will need to be randomised into the trial. This would require 135 deaths in either treatment arm.

The data reviewed during the DMC meeting of July 2013 indicated that 2-year survival in the control arm is not as hypothesised at the design stage. On consultation with the IDSMC and TSC it was agreed that the recruitment target be increased to 410 patients. It is expected that this goal will be met in July 2014 and the required event rate (270 deaths in total) will be achieved one year later, in July 2015. This is the earliest time at which the TMG predicts sufficient statistical power will be obtained, although, continued assessment of recruitment is required. Note that the hazard ratio (0.71) and error rates of the original design are maintained.

Since the 12% difference is optimistic we will endeavour to detect smaller differences of 10% if recruitment exceeds expectation. A sample size of 520 patients is required to detect a 10% absolute survival difference based on a 2-year survival of 20% (i.e. detection of 10% absolute survival differences of 20%-30%) at the 5% level of significance with an 80% power. Whilst this is larger than the original estimate, it satisfies the primary and secondary endpoints. This would require 190 deaths in either treatment arm. Also in the event that the control group exceeds expectation, 520 patients would also allow the detection of 12% differences if the 2 year survival rate for the control group is anything between 20% to 40%. This will be a decision for the IDSMC.

9.3 Analysis

The primary analysis will be comparison of overall survival across treatment groups, calculated from the time of randomisation to the date of death (or censor date). All analysis will be on an intention to treat basis. Comparison of survival estimates will be by log-rank analysis. Toxicity and response rates will be compared across treatment groups using Pearson's chi-square test. QoL scores will be calculated according to the EORTC C30 manual and EuroQoL guidelines and compared across treatment groups using standardised area under the curve analyses and Mann-Whitney tests. Cox proportional hazards models will be undertaken to determine prognostic factors and their influence on survival and provide an adjusted treatment effect by important prognostic and stratification factors.

9.4 Interim Analyses

The only interim analyses will be for the Independent Data and Safety Monitoring Committee (IDSMC) who will review the data 6 months after the first patient is recruited into the trial or after the first 30 patients are recruited, which ever is sooner. It will then meet at approximately annual intervals or more frequently as required. The IDSMC will also decide whether to increase the sample size to detect a 10% absolute survival difference based on a 2-year survival of 20%.

The IDSMC will be asked to give advice on whether the accumulated data from the trial, together with results from other relevant trials, justifies continuing recruitment of further patients. A decision to discontinue recruitment, in all patients or in selected subgroups, will be made only if the result is likely to convince a broad range of clinicians including participants in the trial and the general clinical community. If a decision is made to continue, the IDSMC will advise on the frequency of future reviews of the data based on accrual and event rates. The IDSMC will make recommendations to the Trial Steering Committee (TSC) as to the continuation of the trial. Depending on the success of recruitment into the trial the IDSMC will also review whether to increase the sample size to detect a 10% absolute survival difference based on a 2-year survival of 20%.

9.5 Milestones

The study will be adopted by the National Cancer Research Network. We aim to recruit 410 patients by July 2014. Follow-up will continue until death or withdrawal from study for any other reason. All patients (including those withdrawn from study) will be followed up by ONS (Office of National Statistics) flagging, which will provide copies of patient's death certificates. The planned initiation date was October 2005. However the trial actually opened to recruitment at the first

centre in March 2006. The planned completion of enrolment is July 2014 and planned study completion 2019.

March 2006: trial open to recruitment

30 recruited or 6 months after 1st recruited (whichever sooner): 1st report to IDSMC

Annually thereafter (more frequently if required): report to IDSMC

410 recruited (planned 2014):

Minimum of 1 year after trial closed to recruitment

Minimum of 5 years after trial closed to recruitment

close trial to recruitment

final analysis of 2 year survival

final analysis

10 STUDY PROCEDURES

10.1 Pre-randomisation (Baseline) Evaluations

Pre-randomisation evaluations should be carried out as outlined in Section 6.2 The inclusion and exclusion criteria will be checked at the registration telephone call. Patients will be randomised prior to treatment and treatment allocations will be given during the call.

10.2 Randomisation Procedures

Patients satisfying the entry criteria of the study will be randomised into the study. The Trials Centre will then send confirmation of the patient's inclusion in the trial and the treatment allocation and patient trial number.

To randomise a patient the investigator should:

- Obtain patient's written informed consent to participate in the study
- Complete the Randomisation Form
- Contact the CRCTU in Birmingham by telephone.
 - **2**: [name] or [name] (9am- 5pm Monday to Friday) [contact] hours)
- Record in the patient's notes, patient details: unique patient trial number allocated & treatment allocation.
- Send a copy of the Patient Consent Form by post to the BILCAP study office
- Send the original Randomisation Form by post to the BILCAP study office (with extra
 details added e.g. trial number, treatment allocation).
- **Send** the patient's GP a letter indicating their participation in the study.
- File the original Patient Consent Form in the Investigator Site Folder
- File copies of the Randomisation Form, randomisation confirmation report & GP Letter in the Investigator Site Folder
- Enter patients details into Enrolment Log

10.3 Study Start-Up and Core Documents

Centres wanting to participate in the study should contact the **BILCAP Study Office** to obtain information. The principal investigator at each centre must ensure that the protocol has site specific approval (SSA) by the relevant Local Research Ethics Committee (LREC) and should provide the study office with the following core documentation, and attend an initiation visit or teleconference/telephone call before the site becomes activated:

- The site contact details
- Clinical Study Site Agreement signed by principal investigator at the centre & R&D/Trust
- A current signed and dated copy of each participating investigator's CV
- Site responsibilities sheet with signatures
- The R&D/Trust approval letter
- Application for SSA

10.4 Forms and Data Collection

All study data will be recorded on the case report forms (CRFs) provided. The CRFs must be completed and signed by the Investigator, or designee, as soon as the requested information is available and the CRF pages returned promptly to the **BILCAP Study Office**. In all cases it remains the responsibility of the Investigator for the timing, completeness, legibility and accuracy of the Case Report Forms and he/she will retain a copy of each completed form and each QoL booklet and capecitabine patient diary. The investigator will supply the study office with any required background data from such records. Data reported on the CRFs should be consistent with the source data in the medical notes, or the discrepancies should be explained.

Entries should be made in ballpoint pen on the CRFs provided in black or blue ink and must be legible. Any errors should be crossed out with a single stroke, the correction inserted and the change initialled and dated by the Investigator or designee. If it is not clear why a change has been made, an explanation should be written next to the change. Typing correction fluid should not be used.

